### Examples of an AE:

- Exacerbation of a chronic or intermittent pre-existing condition including either an increase in frequency or intensity of the condition.
- Significant or unexpected worsening or exacerbation of the condition/indication under study.
- A new condition detected or diagnosed after study device administration even though it may have been present prior to the start of the study.
- Pre- or post-procedure events that occur as a result of protocol-mandated procedures (e.g., invasive protocol-defined procedures, modification of a subject's previous treatment regimen).

### An AE Does NOT Include:

- Medical or surgical procedures. The medical condition that leads to the procedure is the AE.

- Hospital admissions where an untoward medical occurrence did not occur.
- Day to day fluctuations of pre-existing disease or conditions present or detected at the start of the study that do not worsen.
- The condition/indication being studied or expected progression, signs, or symptoms of the condition/indication being studied unless more severe than expected for the subject's condition.
- Post-operative findings of swelling or pain within two (2) weeks of the initial procedure, unless deemed by the physician as of greater severity than expected.

#### 10.4.

#### **Follow-Up of Adverse Events**

After the initial AE report, the investigator is required to proactively follow each subject until the event resolves. All AEs documented at a previous visit that are designated as ongoing will be reviewed at subsequent visits/contacts.

Adverse events will be followed until resolution, until no further changes in the event are expected (i.e. the point at which a subject experiencing a critical adverse event is treated successfully and stabilized even though he/she may continue to experience lingering sequelae that may never resolve), until the subject is lost to follow-up, or until it is agreed that further follow-up of the event is not warranted (e.g. non-serious, study therapy unrelated, mild or moderate adverse events ongoing at the subject's final study visit).

New or updated information shall be recorded by completing an AE follow-up CRF.

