##### **6.4.1. Voluntary Withdrawal by Subject**

Study participation is voluntary and subjects may withdraw at any point during the study. If a subject withdraws from the study, the investigator will make all reasonable efforts to determine the reason for the subject's withdrawal and will document the reason on the applicable form. After a subject withdraws from the study, no effort will be made to replace or follow the subject.

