##### **6.4.2. Withdrawal by Investigator**

The investigator may withdraw subjects from the study for many reasons, including but not limited to the following:

- Occurrence of a serious adverse event
- Investigator's discretion to withdraw subject for safety reasons
- Subject noncompliance with visits and/or assessments
- Subject is lost to follow-up (as defined per section 6.4.3)

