##### **6.4.3. Lost to Follow-Up**

Subjects will be defined as lost to follow-up when the following procedures have been documented in the subject's source documentation and End of Study CRF:

- At least 2 phone calls made on separate dates to the subject are not returned
- A certified letter is sent to the subject's last known address and the subject does not reply after 30 days

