##### **6.4.4. Documentation of Study Completion Status**

The completion status of the subject (e.g. completed per protocol, subject withdrawal, device removed, death, lost-to-follow-up, or other reason) should be recorded and the reason for withdrawal, if applicable, should be documented in the source documentation.

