## **10.3. Documentation of Adverse Events**

All adverse events will be documented in the source documentation. Beginning after the study procedure has taken place, all AE's, including those measured, observed or volunteered, will be recorded on the applicable case report form. The investigator will review all documentation (e.g., hospital progress notes, laboratory, or diagnostic reports) relative to the event being reported. The investigator will then record all relevant information regarding an AE onto the study CRF.

The investigator will attempt to establish a diagnosis of the event based on signs, symptoms, and/or other clinical information. In such cases, the diagnosis should be documented as the AE and not the individual signs and symptoms.

When reporting an AE, the investigator will evaluate the event for duration, intensity, relationship and outcome.

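### Section 6.4.1 stops all follow-up of a subject who withdraws voluntarily, but withdrawal is not among the four points at which section 10.4 lets adverse event follow-up end

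*Combined protocol and SAP*

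**What the plan says.** Section 6.4.1 covers subjects who choose to leave. It asks the investigator to make reasonable efforts to find and document the reason, and then states: "After a subject withdraws from the study, no effort will be made to replace or follow the subject". No exception is made for an AE that is still open.

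Section 10.4 sets the duty for AEs. It opens with "the investigator is required to proactively follow each subject until the event resolves" and has ongoing events reviewed at later visits or contacts. Its second paragraph gives the points at which follow-up may end. The first two are in "Adverse events will be followed until resolution, until no further changes in the event are expected", and the other two are in "until the subject is lost to follow-up, or until it is agreed that further follow-up of the event is not warranted". The example given for the last is a non-serious, unrelated, mild or moderate event still present at the final study visit.

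Three other sections bear on the point:

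- Section 6.4.2 lists reasons for which the investigator may withdraw a subject, and the first is "Occurrence of a serious adverse event". It gives no rule on what happens to the event afterwards.
- Section 10.3 says that when an AE is reported, "the investigator will evaluate the event for duration, intensity, relationship and outcome".
- Section 3.1.3 names adverse events and the between-group comparison of complication rates as the safety endpoints.

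**The concern.** The two rules give opposite instructions for a subject who withdraws with an unresolved event. Take a subject who leaves with an unresolved deep infection or foreign body reaction; section 9.1 lists infection and foreign body reaction as potential risks of suture anchors. Section 10.4 keeps that event under follow-up, and section 6.4.1 tells the site to make no effort.

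What is at stake is the later course of the event: how it ended, how severe it became, and whether the device was removed. Subjects who leave because of a complication are likely to be those whose events matter most for safety, so outcomes lost in this way are unlikely to be missing at random. Two coordinators at the same site could also handle identical cases differently, each with a section of the protocol in support.

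The point concerns AE outcomes only. It is separate from whether the 24-month CT is obtained after withdrawal.

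**Working it through.** The point turns on wording, so the check is to set the sections side by side and ask whether any of them removes the conflict.

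1. **Is withdrawal one of the end points in 10.4?** No. The four are resolution, a stable state, loss to follow-up, and agreement that continuing is unnecessary.

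2. **Could withdrawal count as loss to follow-up?** No. Section 6.4.3 defines that status by failed contact: "At least 2 phone calls made on separate dates to the subject are not returned", together with a certified letter unanswered after 30 days. A subject who tells the site that they are leaving has been reached. Section 6.4.4 also lists the two as separate statuses: "completed per protocol, subject withdrawal, device removed, death, lost-to-follow-up, or other reason".

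3. **Could the fourth end point cover it?** In part. The example in 10.4 is only an example, so agreement could close many mild or moderate events at exit. The agreement concerns the particular event, however, and the example does not naturally extend to a serious, severe or device-related one. For those the conflict remains.

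4. **Does section 15.1 settle it?** No. It has the investigator ensure adequate care for trial-related AEs both during and after participation. That is a duty of care, and it does not say that the outcome must be recorded as study data.

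5. **Does 6.4.1 apply to every withdrawal?** No. The sentence stands under voluntary withdrawal. Section 6.4.2 contains no such sentence, so nothing there displaces 10.4 when the investigator withdraws a subject.

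6. **Does any section say which rule prevails?** None does.

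**Can the number of affected subjects be derived?** The only relevant figure is the drop-out allowance in section 14. It reproduces: 2 × 27 = 54 evaluable subjects, and 54 / (1 − 0.20) = 67.5, rounded up to 68. The allowance is 0.20 × 68 = 13.6, or about 14 subjects. The plan does not divide these between withdrawal and loss to follow-up (the latter being an end point that 10.4 accepts), and it does not say how many would leave with an open AE. No estimate follows.

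**The case against.** The strongest case on the other side is that this is a small drafting tension with little effect on the safety results. Several parts of that case stand.

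- A reader might infer that 10.4 requires every AE to be followed until it resolves, so that every open event at withdrawal breaches it. The next paragraph of 10.4 does not support this, because it allows three other end points. The conflict is firm only for events that could not reasonably be closed under them.
- A reader might also infer that 6.4.2 contradicts 10.4, because it allows withdrawal for a serious AE. It does not. It is silent, and the general duty in 10.4 is left in place.
- A further inference would be that an event turning serious after exit would never reach the IRB. Section 11.1 counts its ten working days from learning of the event and is not limited to active participants, and the continuing care in 15.1 is a route by which the investigator may learn of it. The supportable statement is that the site may not learn of it.
- A complication recorded before exit has already occurred and stays in the complication rate. What may be lost is its outcome and later course.
- The consent pages are not available for this review, so nothing can be said about what subjects are told of contact after withdrawal.

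It can also be argued that 6.4.1 was meant to cover scheduled visits only. That may be the intent, but the text does not say so, and saying so is most of the remedy. None of these arguments reconciles 6.4.1 with 10.4 for a serious, severe or device-related event open at voluntary withdrawal.

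**Conclusion.** The concern holds for voluntary withdrawal. There, 6.4.1 and 10.4 cannot both be followed for an AE that is open at exit and has met none of the four end points. A site that follows 6.4.1 may leave the final outcome, a later worsening or a device removal unrecorded. For withdrawal by the investigator the protocol has a gap, which the same amendment should close.

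The effect is on the completeness of AE outcomes. The primary endpoint and the sample size are untouched. A percentage of an arm with missing safety outcomes would be tempting to quote, but it would need an assumed number of open events and an assumed split between arms, and the documents support neither.

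The conclusion rests on two readings: that the word follow in 6.4.1 carries its ordinary, unrestricted meaning, and that withdrawal and loss to follow-up are distinct statuses, as 6.4.3 and 6.4.4 treat them. The change is worth making because the conflict touches safety data and costs little to remove.

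**What to change.** Reconcile the sections with two sentences:

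- In 6.4.1, limit the no-follow sentence to scheduled study assessments.
- In 6.4.1 and 6.4.2, state that an AE open at withdrawal stays under the existing list of end points in 10.4, by telephone or medical record, unless the subject refuses that contact. The outcome is recorded on the AE follow-up CRF that 10.4 already provides for.

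No new form, visit or imaging is needed. The cost is the amendment itself and a few calls or record checks for subjects who leave with an open event. The consent form should be checked to see that it describes such contact.

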### **11. Reporting of Adverse Events**

#### 11.1.

#### **Investigator Adverse Event Reports**

Investigators are responsible for reviewing all SAEs, ADEs, SADEs, and UADEs, determining the relationship to the device and documenting on the appropriate CRF. All SAEs, ADEs, SADEs and UADEs must be reported by the investigator to the IRB (as applicable) as soon as possible but no later than ten (10) working days after learning of the event. The investigator must submit a detailed report that will identify the description of symptoms, classification of the event, date of onset, severity, treatment, and outcome. Supporting medical records may be obtained as an adjunct to an adverse event report and placed in the subject's study file.

All AEs will be categorized as mild, moderate or severe based on the following definitions:

**Mild:** The subject is aware of the sign or symptom, but finds it easily tolerated. The event is of little concern to the subject and/or little clinical significance. The event is not expected to have any effect on the subject's overall health or wellbeing.

**Moderate:** The subject has discomfort enough to cause interference with or change in usual activities. The event is of some concern to the subject's health or wellbeing and may require medical intervention and/or close follow-up.

**Severe:** The adverse event interferes considerably with the subject's usual activities. The event is of definite concern to the subject and/or poses substantial risk to the subject's health or wellbeing. The event is likely to require medical intervention and/or close follow-up and may be incapacitating or life threatening. Hospitalization and treatment may be required.

## **12. Source Documentation**

Investigators are responsible for obtaining and maintaining complete subject health information in the medical record for each subject and each assessment in the protocol (source documents). Source documents include all information in original records and certified copies of original records of clinic findings, observations or other activities in the study necessary for the reconstruction and evaluation of the trial. Source data are contained in source documents (e.g., hospital records, clinic and office charts, memoranda, dispensing records, subject questionnaires, clinic evaluation transcriptions, operative notes, x-rays, radiology reports, blood collection and shipment records, research subject files, etc.)

## **13. Disclosure of Data and Data Security**

### **13.1. Data Security and Confidentiality**

The clinical data obtained in this study will be kept private. In any sort of published report, there will be no identifying information. Records for this study may be reviewed by the IRB and/or other government agencies may inspect and photocopy all medical records applicable to involvement in this study.

Participating subjects will be asked to sign a consent form that includes an authorization to use and/or disclose personal health information. Subjects are free to refuse authorization to transfer personal information. If the subject chooses not to agree to this authorization, the subject is not eligible to participate in the study. Personal information (including sensitive personal health information, such as medical history) if relevant to the study will be reviewed, collected in a computer database, stored in electronic or manual files, audited, and / or otherwise processed by the investigator, regulatory agencies, and other persons and/or agencies as required by law or allowed by applicable regulations.

## **14. Statistical Procedures**

To determine sample size, we have powered our study (a-priori) using test of proportions, assuming inequality, with two independent groups. The primary outcome measure used will be an ossification quality score at 24 months. The ossification quality score is an ordinal measure of quality of bone reabsorption that is divided into four progressive groups. Quality score 1 reflects “little or no bone ossification”, Quality score 2 reflects “Some ossification; discontinuous or with a wide lucent rim”, Quality score 3 reflects “Ossification with a thin lucent rim”, and Quality score 4 reflects “Good ossification; border of tract vague”. For this study, Quality scores 1 and 2 will be merged (defined as low quality ossification) as will Quality scores 3 and 4 (defined as high quality ossification).

For a conservative 85% proportional Quality score measures of 3 and 4 (high qualify ossification) for the HEALICOIL™ REGENESORB group and a 49.9% proportional Quality score measures of 3 and 4 (high qualify ossification) for the TWINFIX™ Ultra HA group (Barber, Dockery and Cowden. Arthro. 2013).

A two group chi-square test with a 0.050 two-sided significance level will have 80% power to detect the difference between a Group 1 proportion,  $\pi_1$ , of 0.499 and a Group 2 proportion,  $\pi_2$ , of 0.850 (odds ratio of 5.689) when the sample size in each group is 27 subjects by end of 24 months. Since a drop-out rate of 20% is expected from baseline, we will target total of 68 subjects to meet the time-oriented goals of the analyses.

The TWINFIX Ultra HA differs from the reference device (Healix BR, DePuy Mitek) in material properties and characteristics. TWINFIX Ultra HA is composed of a Poly-L-Lactide/Hydroxyapatite

(PLLA/HA) blend while the reference device is a poly-l-lactideco-glycolide- $\beta$ -tricalcium phosphate and calcium sulfate (PLLA/PGA- $\beta$ -TCP, Ca So4) blend. Based on our pre-clinical testing the PLLA/HA device takes longer to degrade when compared to a device composed of PLLA/PGA. We therefore predict that our control device (TWINFIX) will not meet the hypothesized proportional score of 49.9%.

## **15. Investigator Responsibilities**

### **15.1. Medical Oversight**

At all times the investigator is responsible for the rights, safety and welfare of subjects under the investigator's care. The investigator is directly responsible for the ongoing medical care of subjects enrolled in this study, as well as for all study-related medical decisions. During and following a subject's participation in the study, the investigator should ensure that adequate medical care is provided to a subject for any adverse events, including clinically significant laboratory values if applicable, related to the trial. The investigator should inform the subject when medical care is needed for all intercurrent illness(es) of which the investigator becomes aware. The investigator should inform the subject's primary physician about the subject's participation in the study, if the patient has a primary physician and if the subject agrees to the primary physician being informed.

### **15.2. Investigator Records**

The Investigator will maintain complete, accurate and current study records, including but not limited to the following materials:

1. Correspondence with other Investigators or the IRB;
2. Study Subject Records including signed and dated informed consent forms, all source documentation, subject CRFs, queries and records of exposure of each subject to the device;
3. All relevant observations, including records and reports concerning adverse effects (whether anticipated or unanticipated);
4. Current study protocol
5. The approved blank Informed Consent form and blank Subject CRFs;
6. Certification that the Investigational Plan has been approved by all of the necessary approving authorities; and
7. Signed/dated current CV's of the Principal Investigator and any participating Co-Investigators.

